10.5.12 Healthcare Resource Utilization

Summary statistics of the number of subjects who had a doctor office visit (non-study scheduled) or emergency room visit, or a hospitalization after signing informed consent, and the number of subjects hospitalized in a higher level of care unit by type (e.g., Intensive care unit, Coronary care unit, Other, Missing), the number of days in higher care units during the study will be presented by treatment group. Number of days of hospitalization will be defined as (hospitalization end date – hospitalization start date) + 1. If hospitalization has unknown start or/and end date, it will be counted in ‘Missing’ category.

Reasons for inpatient hospitalization will be summarized categorically using number and percentage of subjects with the following categories:

- Adverse Events
- Protocol-driven procedure (e.g., bone marrow aspiration)
- Non-protocol driven assessments or procedure (e.g., ultrasound)
- Transfusion (e.g., RBC, platelets)
- Procedure planned prior to signing informed consent (e.g., coronary arteriogram)
- Elective procedure for a pre-existing condition (e.g., hernia repair)
- Social, technical or practical reason in the absence of an Adverse Event (e.g., travel distance from the clinic prohibitive for study participation).

A listing will be provided for healthcare utilization.

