**Table 2: Study Endpoints (Continued)**

Endpoint	Name	Description	Time of Endpoint Measurement			Timeframe
			24 weeks	48 weeks	Long -Term	
Other Efficacy Endpoints	• Mean change from baseline in total hip and lumbar spine bone mineral density by DXA	Total hip and lumbar spine BMD by DXA	X	X	X	Screening up to last DXA scan visit
	• Mean change from baseline in myocardial iron by MRI	Myocardial iron by T2* MRI	-	X	X	Screening, as per Table 3 , up to last MRI for T2* measurement visit.
	• Mean change in Quality of Life measures	Self-reported QoL assessed by TranQoL, and SF-36 questionnaires	X	X	X	Screening, as per Table 3 , up to last QoL measurement visit.
	• Healthcare resource utilization	Medical resource utilization (refer to Section 9.6.3.7)	X	X	X	Screening until End of Study
	• Proportion of subjects who are transfusion independent for $\geq 8$ weeks during treatment	RBC transfusions	X	X	X	Dose 1 Day 1 through 3 weeks post last dose
	• Duration of reduction in transfusion burden	RBC transfusions (refer to Section 9.6.2)	X	X	X	Dose 1 Day 1 until last visit date or the date of discontinuation
	• Duration of transfusion independence	RBC transfusions (refer to Section 9.6.2)	X	X	X	Dose 1 Day 1 until last visit date or the date of discontinuation
	• Time to erythroid response	RBC transfusions (refer to Section 9.6.3.9)	X	X	X	Dose 1 Day 1 through last visit in the double-blind Treatment Period
	• Post-baseline transfusion events frequency versus placebo	RBC transfusions	X	X	X	Dose 1 Day 1 through 3 weeks post last dose

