##### 3.1.1. Screening/Run-in Period

Upon giving written informed consent, the subject enters the Screening/Run-in Period to determine eligibility. Subjects' identification (ID) number will be allocated via Interactive Response Technology (IRT) system as detailed in Section 7.3. The Screening/Run-in period will last at least 12 weeks. During the Screening/Run-in Period, the subject will undergo safety and other assessments to determine eligibility for the study as detailed in Table 3, Table of Events. Subject eligibility will be reviewed with the Sponsor, prior to the subject's randomization via the IRT. Re-screening is allowed and a new subject ID number will be assigned.

The regularly transfused  $\beta$ -thalassemia subjects must have at least 24 weeks of documented transfusion history available (including Hb levels prior to each transfusion, the number of units transfused, the date of transfusion) prior to randomization. Twelve weeks of transfusion history will be collected prospectively during the Screening/Run-in Period, in addition to the 12 weeks historical retrospective data that will be further recorded in the subject's electronic case report form (eCRF).

The 24-week transfusion history prior to randomization into the Treatment Period will be used to determine the baseline RBC transfusion burden as well as the mean pre-transfusion Hb value for each study subject.

Subjects will be stratified prior to randomization based on:

1. Geographical regiona (Viprakasit, 2013):
  - North America and Europe
  - Middle East and North Africa
  - Asia-Pacific

a See Appendix E for list of countries within each region.

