### 3.2. Study Duration for Subjects

Study participation for each subject includes a Screening/Run-in Period of at least 12 weeks, a 48-week placebo-controlled double-blind Treatment Period, followed by a double-blind Long-term Treatment Period and an Open-label Phase. The Post-treatment Follow-up Period will last 156 weeks (ie 3 years) post last dose.

The study will be comprised of the following periods:

**Screening/Run-in Period**, will be at least 12 weeks prior to randomization.

**Treatment Period**, which will be approximately 48 weeks, independent of Dose Delays beginning with Dose 1 Day 1.

**Long-term Treatment Period**, the double-blind Long-term Treatment Period will continue until all subjects complete 48 weeks of double-blind treatment or discontinue before reaching 48 weeks of the double-blind Treatment Period, or at the time the study is unblinded (per DMC recommendation), whichever occurs first.

**Open-label Phase**, the Open-label Phase will continue until all subjects initially assigned to luspatercept in the double-blind Treatment Period, complete the total treatment duration of 5 years from subjects' Dose 1 Day 1 in the treatment period of this ACE-536-B-THAL-001 study or discontinue earlier.

**Post-treatment Follow-Up Period**, all subjects who discontinue treatment will undergo a 156-week (ie 3 years) Post-treatment Follow-up Period, following the last dose of IP. Additional information on the visits to complete when subjects discontinue treatment is presented in Section 3.1.5.

**End of Treatment for each individual subject** is defined as the date of the last visit in the Treatment Period, the Long-term Treatment Period, or in the Open-label Phase, whichever is the later date.

**End of Study for each individual subject** occurs at the time of completion of the 156-week Post-treatment Follow-Up Period or at the time of the end of the Open-label Phase (if subjects are still on treatment, see the description above) or at the time of End of Trial as defined below.

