**Table 3: Table of Events (Continued)**

Assessments	Section	Screening/ Run-in Period Week -12 to Day -1	Treatment Period (double-blinded)				Long-term Treatment Period  (double- blinded) every 3-wk visits from Week 49 (ie, Dose 17 if no dose delays) /Day 1 (± 5 days)	Open-label Phase, every 3-wk visits from unblinding (± 5 days)		Day 22 Post Last Dose/ D/C 	Post-treatment Follow-up Period (± 7 days)				
			Luspatercept/ placebo Dose 1 Schedule (+7 days)		Luspatercept/placebo Doses 2 up to max 48 weeks Treatment (± 3 days)			Dose 1 for Placebo, Discont. 	Dose X Day 1 		Follow- up Week 9 (from last dose) 	Only if  Early Discont. – Follow-up Visits weeks 24, 48, 72, 96, 120, 144 (from last dose) 	All subjects: Follow- Up Visits weeks 24, 48, 72, 96, 120, 144 (from last dose) 	End of Study  / Follow- up week 156 (from last dose) 	
			Day 1	Day 1	Day 8	Day 15									
QoL Questionnaire (TranQoL, SF36), assessments to be performed independent of Dose Delays	6.1, 6.1.1, 6.2, 6.3, 6.11	X (within 4 wks prior Dose 1 Day 1)	-	X (wk 12, 24, 36 & wk 48)	-	-	every 12 weeks	-	-	-	-	-	-	-	
Healthcare Resource Utilization	6.1 to 6.6	Record on ongoing basis, until 9 weeks Post-last Dose 													
Serum Ferritin (predose, central lab; screening value at least 12 weeks prior to randomization; in Open-label Phase – use local labs)	6.1 to 6.6	X (within 4 wks prior Dose 1 Day 1)	X	X	-	-	X  (every 4 doses)	X	-	X	X	-	-	-	

CCI

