3.2.2 Extended Secondary Objectives

The following secondary objectives will be conducted in this final CSR:

- To evaluate the mean change from baseline in liver iron concentration (LIC) versus placebo up to final database lock
- To evaluate the mean change from baseline in mean daily dose of iron chelation therapy (ICT) used versus placebo up to final database lock
- To evaluate the mean change from baseline in serum ferritin versus placebo up to final database lock
- To evaluate the effect of luspatercept on osteoporosis/osteopenia, total hip and lumbar spine measured by bone mineral density (BMD) versus placebo up to final database lock
- To evaluate mean change from baseline in myocardial iron versus placebo up to final database lock
- To evaluate the effect of luspatercept on healthcare resource utilization versus placebo up to final database lock
- To evaluate the proportion of subjects who are transfusion independent for ≥ 8 weeks versus placebo up to final database lock

- To evaluate the duration of reduction in transfusion burden or transfusion independence up to final database lock
- To evaluate the time to erythroid response up to final database lock
- To evaluate the post-baseline transfusion events frequency versus placebo up to final database lock
- Evaluate the safety of luspatercept versus placebo up to final database lock.

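### Healthcare resource utilisation is counted from informed consent, so run-in events before randomisation are tabulated as outcomes of luspatercept or placebo

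*SAP*

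**What the plan says.** The objective in SAP 3.2.2 is comparative: "To evaluate the effect of luspatercept on healthcare resource utilization versus placebo up to final database lock". HRU is listed among the extended secondary efficacy endpoints in SAP 4.2.2.3.

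The analysis in SAP 10.5.12 covers subjects with an unscheduled office visit or "emergency room visit, or a hospitalization after signing informed consent, and the number of subjects hospitalized in a higher level of care unit", and adds that "the number of days in higher care units during the study will be presented by treatment group". Reasons for inpatient admission are also tabulated, and transfusion is one of the listed reasons.

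Protocol Table 2 gives the HRU timeframe as "Screening until End of Study". The Table of Events says "Record on ongoing basis, until 9 weeks Post-last Dose", and protocol 6.1 lists HRU among the screening items. These passages differ on when the window ends, but none starts it at first dose.

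On the run-in, protocol 3.1.1 states: "Upon giving written informed consent, the subject enters the Screening/Run-in Period to determine eligibility". It adds: "The Screening/Run-in period will last at least 12 weeks". Protocol 3.2 repeats that this period "will be at least 12 weeks prior to randomization". Protocol 6.2 puts the time from consent to first dose at approximately 12 weeks.

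**The concern.** Nothing that happens between consent and randomisation can be caused by either treatment. Under SAP 10.5.12 it still makes the subject an HRU case in the arm assigned later. Anyone with a run-in event of a given type is already a case of that type and cannot show a benefit on that subject-level count, however few events follow.

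Run-in events are plausible. Eligibility allows no transfusion-free period longer than 35 days in the 24 weeks before randomisation, so every eligible subject is transfused during the run-in. At a site that admits patients for transfusion, a subject would be a hospitalisation case before randomisation. Fewer transfusions are also a route by which protocol 1.3.2.2 expects treatment to affect resource use.

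At stake is how readable a secondary efficacy summary is. No confirmatory test is involved.

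**Working it through.** The plan gives no HRU event rate, test or sample size, so there is no planned figure to reproduce. Two checks apply.

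**Where the window starts, against the plan's other event-type endpoints**

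- HRU: consent (SAP 10.5.12) or screening (protocol Table 2). No baseline HRU is defined.
- Transfusion burden: the SAP 5.1 baseline runs from Day -83 to Day 1, and the first post-baseline interval starts on Day 2. SAP 18.2 has no Day 0, so the baseline is 83 + 1 = 84 days, or 12 weeks, the same as the minimum run-in.
- Transfusion event frequency: Table 2 starts it at Dose 1 Day 1, and SAP 10.5.10 puts the pre-dose frequency in the model as a covariate.
- Treatment-emergent adverse events: from first dose (SAP 11.1).
- SAP Section 10 sets an upper cutoff for final-CSR efficacy data but no lower bound.

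Of these, HRU alone mixes pre-dose and post-dose events.

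**Size**

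Inputs from the documents: run-in of 12 weeks (the minimum); follow-up W of 48 weeks (protocol 3.1.2), 96 weeks (last LIC time point analysed for placebo, SAP 10.5.2) or 228 weeks (last transfusion interval in SAP 5.1).

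Assumptions, none from the documents: constant event rates, equal in both arms before dosing; a true on-treatment rate ratio RR of 0.50 or 0.70; placebo rates of 0.1 to 1.0 events per year.

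Run-in share = 12/(12 + W):

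- W = 48: 12/60 = 20.0%
- W = 96: 12/108 = 11.1%
- W = 228: 12/240 = 5.0%

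Apparent rate ratio = (12 + RR × W)/(12 + W). Adding the run-in leaves a constant placebo rate unchanged, so W here is the luspatercept follow-up.

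- W = 48: RR 0.70 gives (12 + 33.6)/60 = 0.76; RR 0.50 gives (12 + 24)/60 = 0.60.
- W = 228: RR 0.70 gives (12 + 159.6)/240 = 0.715; RR 0.50 gives (12 + 114)/240 = 0.525.

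The subject-level counts are closer to the proportion with any event by Week 48, 1 − exp(−expected events). At 0.3 events per year and RR 0.50:

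- From Day 1: placebo 1 − exp(−0.3 × 48/52) = 0.242, luspatercept 1 − exp(−0.15 × 48/52) = 0.129; risk ratio 0.535.
- From consent: placebo 1 − exp(−0.3 × 60/52) = 0.293, luspatercept 1 − exp(−(0.3 × 12 + 0.15 × 48)/52) = 0.188; risk ratio 0.641.

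Over 0.1 to 1.0 events per year, the risk ratio moves from 0.51–0.61 to 0.61–0.73 (RR 0.50) and from 0.71–0.79 to 0.77–0.85 (RR 0.70). With RR 0.50 the difference in proportions barely moves at 0.1 per year (0.043 to 0.042) but falls from 0.233 to 0.185 at 1.0 per year.

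Unequal follow-up, illustrated with placebo to Week 96, luspatercept to Week 228 and RR 0.70. The ratio of expected events per subject, luspatercept to placebo, is:

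- From first dose: (0.7 × 228)/96 = 159.6/96 = 1.66
- From consent: 171.6/108 = 1.59

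Raw event counts then show more events on luspatercept although its true rate is lower. Including the run-in makes that apparent excess slightly smaller.

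**The case against.** The strongest case against has six parts.

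- *The SAP follows the protocol.* Table 2 starts HRU at screening, so the SAP wording is not a stray slip. This stands: Table 2 has to be aligned as well. It does not justify presenting run-in events as treatment outcomes.
- *The consent phrase may attach only to hospitalisation.* Grammatically it may. Hospitalisation is explicit; office and emergency visits follow on the natural reading and from Table 2, which covers HRU as a whole.
- *The SAP plans counts of subjects and days, with no rate ratio or test.* This stands. The rate ratios above illustrate dilution and are not distortions of a planned output.
- *The final-CSR window is long.* This stands for long-treated subjects, whose run-in share is near 5%. It does not hold for those who stop early.
- *Constant rates are doubtful.* Recent major surgery, thrombosis or stroke needing intervention, and infarction are exclusions, so some subjects admitted during the run-in are never randomised. Run-in admissions may be fewer than their share of time suggests.
- *HRU is descriptive, a listing is planned, and randomisation balances run-in events in expectation.* All true, and this limits the severity.

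A reader might infer that the rule favours one arm, or that it always pulls the result towards no difference. The documents support neither. Run-in events precede assignment, so they favour no arm in expectation. Dilution towards no difference holds cleanly only over an equal window such as 48 weeks; SAP Section 10 stops placebo data at cross-over while luspatercept data continue.

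**Conclusion.** The point holds, at minor severity. At least 12 weeks of pre-randomisation HRU enter a by-arm summary that serves an effect-versus-placebo objective, and nothing in either document separates them out. The run-in is 20% of an equal 48-week window and about 5% of a window to Week 228. The 20% figure should not be carried over to long-treated subjects in the final CSR, where unequal follow-up is the larger difficulty with raw counts. The sizes rest on constant rates, a 12-week run-in and assumed rate ratios; a longer run-in would dilute more. HRU is outside the gate-keeping sequence in SAP 10.1 and 10.3, so no confirmatory conclusion changes.

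**What to change.** - In SAP 10.5.12, count HRU events that start after first dose (after randomisation if untreated), up to the efficacy cutoff or cross-over already set in SAP Section 10. This matches the Day 2 start used for the transfusion endpoints.
- Report HRU from consent to first dose separately, as baseline by arm.
- Align the analysis timeframe in protocol Table 2. Keep collection from screening, which supplies the baseline.
- Because follow-up is unequal, give exposure-adjusted rates or a common 48-week window alongside the counts.

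The cost is a date condition, one extra table block and the Table 2 alignment. SAP 10.5.12 already uses hospitalisation start dates. The counts become smaller, and a note is needed if the primary CSR used the consent-based window, which cannot be checked because its SAP is not among the documents.

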10.6 Completed Subgroup Analysis

The primary, key secondary efficacy endpoints, and the 33% and 50% erythroid response endpoints by ‘rolling’ base interval have been summarized for the following subgroups:

1. Geographic region:
 - North America and Europe
 - Middle East and North Africa
 - Asia-Pacific
2. Age:
 - ≤ 32 years
 - > 32 years
3. Splenectomy:
 - Yes
 - No
4. Sex:
 - Male
 - Female
5. Beta-thalassemia gene mutation grouping:
 - B0/B0
 - Non-B0/B0
6. Baseline transfusion burden
 - ≤ 6 units/12 weeks
 - > 6 units/12 weeks
7. Mean pre-transfusion hemoglobin at baseline
 - < 9 g/dL
 - ≥ 9 g/dL

8. Baseline liver iron content
 - ≤ 3 mg/g dry weight
 - $> 3 - \leq 7$ mg/g dry weight
 - $> 7 - \leq 15$ mg/g dry weight
 - > 15 mg/g dry weight
9. Baseline transfusion burden (units/24 weeks): for endpoints based on 24-week rolling method only
 - Low transfusion burden (≤ 10 units/24 weeks)
 - Medium transfusion burden ($> 10 - \leq 15$ units/24 weeks)
 - High transfusion burden (> 15 units/24 weeks);
10. Baseline transfusion burden (units/12 weeks): for endpoints based on 12-week rolling method only
 - Low transfusion burden (≤ 5 units/12 weeks)
 - Medium transfusion burden ($> 5 - \leq 7$ units/12 weeks)
 - High transfusion burden (> 7 units/12 weeks);

No further subgroup analysis will be conducted in the final CSR.

10.7 Missing Data Imputation

In case of any missing data for RBC transfusion units records and MRI liver iron content, imputation will be applied for each section.

The imputation for RBC transfusion units is stated in Section 10: if at the time of data summary, a subject's efficacy cutoff date is before the end of the 12-week interval or a subject has any invalid transfusion records (i.e., transfusion unit not available) during the specified 12 week interval, this subject will be included in the analysis as a non-responder.

The imputation logic for missing LIC value is stated in Section 10.5.2: the value of LIC will be either the value collected from eCRF or the value derived from T2*, R2* or R2 parameters depending on which techniques and software were used for MRI LIC data acquisition.

11. SAFETY ANALYSIS

The purpose of this section is to define the safety parameters for the study. All summaries of safety data will be conducted using the safety population. The safety analysis includes adverse events (AEs), clinical laboratory tests, vital signs, electrocardiogram (ECG), cardiac Doppler or Multi Gated Acquisition Scan (MUGA), and antidrug antibody (ADA) testing. In addition, pregnancy test and menstrual status assessments will be provided for female subjects.

If not otherwise specified (for example, AEs), safety summaries will use all collected records including data collected after the primary database lock. The safety analyses will be summarized by the following treatment groups:

- Luspatercept excluding cross-over: original luspatercept patients
- Placebo: original placebo patients
- Luspatercept cross-over only: original placebo patients who crossed over to luspatercept
- Luspatercept including cross-over: all the patients who took luspatercept in DB and/or OL periods.

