- All listings will display original collected values, cases with special marks (i.e., <500) will be listed as it is. The special mark will be removed if the value is used for calculation in tables.
- All analysis and summary tables will have the analysis population sample size (i.e., number of subjects) if not otherwise specified;
- All summary tables will be displayed by treatment (“Luspatercept + BSC” and “Placebo + BSC”), the “Total” group will be added for sections if specified;
- The day of the first dose of IP will be defined as Day 1; for erythroid response related endpoint, if a subject is not treated, the randomization date will be used as Day 1.
- In general, if not otherwise specified, baseline value will be defined as the last value (including “unscheduled”) on or before the date of the first dose of IP (if collecting time is available, date/time will be used to compare with first dosing date/time to identify baseline record, if there is no time available, only date will be used); if multiple values are present for the same date/time, the average of these values will be used as the baseline. For subjects who were not treated, the value on or prior to randomization date will be used. Specifically, for the laboratory hematology parameter ‘Leukocytes’, the baseline is defined as the highest value between screening visit and dose 1 day 1 visit.
- For data handling in change from baseline and shift tables (except for MRI and DXA parameters), “unscheduled” visits will be grouped with the closest scheduled visit based on assessment date. The average will be used as value for that scheduled visit in change from baseline tables; the worst category will be used in shift tables. If an unscheduled visit has equal distance to two scheduled visits, it will be grouped with the later visit. Specifically, for ADA titer summary, the titer value won’t be averaged if an “unscheduled” visit is mapped to the closest scheduled visit. The titer for “unscheduled” visit will only be used for summary if the original scheduled visit has no titer result.
- For RBC transfusion related efficacy endpoints summary, the 12-week interval before Week 48 is defined as:

Baseline 12-week interval: from Day -83 to Day 1;
Week 1 - 12 interval: from Day 2 to Day 85;
Week 13 - 24 interval: from Day 86 to Day 169;
Week 25 - 37 interval: from Day 170 to Day 253;
Week 37 - 48 interval: from Day 254 to Day 337.

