10. EFFICACY ANALYSIS

All efficacy evaluations are conducted using the ITT population, with the exception of Quality of Life analyses that are conducted on the HRQoL evaluable population. Statistical comparisons are made between luspatercept plus BSC vs. placebo plus BSC. Key secondary efficacy results are considered statistically significant after consideration of the strategy for controlling the family-wise Type 1 error rate, as described in Section 10.1, Multiplicity. All statistical tests are 2-sided at the significance level of $\alpha = 0.05$, and the corresponding p-values and 2-sided CIs for point estimates are reported, unless specified otherwise.

For the early treatment discontinued subjects, i.e., patients who did not complete 24 weeks or 48 weeks of double-blinded treatment period, the transfusion records were collected up to 48 weeks or 9 weeks post last dose, whichever was the later date. All the transfusion records collected throughout the entire study period up to the efficacy cutoff date were used in the RBC related efficacy analyses. The efficacy cutoff date for the primary CSR was defined as the minimum date among death date, study discontinuation date, last dose date + 20, and 11MAY2018. For the primary and key secondary endpoints, if at the time of data summary, a subject's efficacy cutoff date was before the end of the 12-week interval or a subject had any invalid transfusion records (i.e., transfusion unit not available) during the specified 12-week interval, this subject was included in the analysis as a non-responder.

All the efficacy analysis for the final CSR will not include the assessments for the placebo patients who crossed over to luspatercept. In other words, the assessments for the placebo patients will be analyzed up to the cross-over timepoint. For those subjects in the original luspatercept treatment, their assessments will be analyzed until the new efficacy cutoff date which is defined as the minimum date among death date, study discontinuation date, last dose date + 20.

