11.1 Adverse Events

Adverse events will be analyzed in terms of treatment-emergent adverse events (TEAEs) which are defined as any AEs that begin or worsen on or after the start of study drug through 63 days after the last dose of IP (i.e., AE start date on or after the first dose date and within last dose date + 63). In addition, an AE that occurs beyond this timeframe and that is assessed by the investigator as possibly related (suspected) to study drug will be considered to be treatment-emergent.

All AEs will be coded using the MedDRA (Version 23.0). The incidence of TEAEs will be summarized by MedDRA SOC and PT. The AE tables will be sorted by SOC and PT (within SOC) in descending frequency within the luspatercept group. If a subject experiences multiple AEs under the same PT (or SOC), then the subject will be counted only once for that PT (or SOC).

The intensity of AEs will be graded 1 to 5 according to the National Cancer Institute Common Terminology Criteria for Adverse Events (CTCAE) Version 4.0. If a subject experiences the same AE more than once with different toxicity grades, then the event with the highest grade will be tabulated in “by grade” tables. In addition, AEs with a missing intensity will be presented in the summary table as an intensity category of “Missing” only if the same event category has no other valid grades.

Tables summarizing the incidence of TEAEs will be generated for each of the following by treatment group (if not otherwise specified, the summary is by SOC and PT):

- TEAEs;
- TEAEs by SOC only;
- Treatment-related TEAEs;
- Serious TEAE;
- Treatment-related serious TEAEs;
- TEAEs by CTCAE maximum severity;
- Treatment-related TEAEs by CTCAE maximum severity;
- TEAE with CTCAE Grade ≥ 3 ;
- Treatment-related TEAE with CTCAE Grade ≥ 3 ;
- TEAEs leading to study drug discontinuation;
- Treatment-related TEAEs leading to study drug discontinuation;
- TEAEs leading to study drug dose reduction;
- Treatment-related TEAEs leading to study drug dose reduction;
- TEAEs leading to study drug dose delay;
- Treatment-related TEAEs leading to study drug dose delay;
- TEAEs leading to death;
- Treatment-related TEAEs leading to death;
- Most frequent TEAEs by PT ($\geq 5\%$ in PT frequency of all subjects or subjects from any treatment group); Most frequent TEAEs by SOC ($\geq 5\%$ in SOC frequency of all subjects); Most frequent TEAEs by SOC and high level term (HLT) ($\geq 5\%$ in HLT frequency of all subjects)

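### For the final CSR the SAP sets no cross-over boundary for safety, so as written open-label luspatercept events in cross-over subjects count under Placebo

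*SAP*

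**What the plan says.** SAP 11 lists four safety columns. Three of them can contain the same person:

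- The comparison column is given as "Placebo: original placebo patients".
- A further column takes a subset of those same people: "Luspatercept cross-over only: original placebo patients who crossed over to luspatercept".
- The last one pools that subset with the subjects assigned to the drug from the start: "Luspatercept including cross-over: all the patients who took luspatercept in DB and/or OL periods".

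All are defined by who the subject is. None has a start or stop date.

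SAP 11.1 defines a treatment-emergent event by one window per subject: "AE start date on or after the first dose date and within last dose date + 63". It speaks of study drug and IP without separating blinded placebo from open-label luspatercept. A later event that is "assessed by the investigator as possibly related (suspected) to study drug will be considered to be treatment-emergent" is added with no end date, again without saying which product is meant. SAP 9.1 runs treatment duration from the first dose of study drug to the last dose plus 20 days, or death, with no break at cross-over.

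For summaries other than adverse events, SAP 11 says that "safety summaries will use all collected records including data collected after the primary database lock". SAP 5.1 takes baseline as the last value "on or before the date of the first dose of IP", which for a placebo subject is the first placebo dose.

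For efficacy the plan does set a boundary. SAP 10 says that "the assessments for the placebo patients will be analyzed up to the cross-over timepoint". SAP 11 and its subsections have no counterpart, although SAP 3.2.2 keeps safety versus placebo, up to the final database lock, as an extended objective.

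**The concern.** Once placebo subjects may take open-label luspatercept, a column defined by original assignment no longer describes placebo. Without a date boundary, the Placebo column of the final safety tables mixes blinded placebo time with luspatercept time, and the cross-over columns take in events from before any luspatercept was given.

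The tables affected include serious and fatal events (SAP 11.1), malignancy and premalignant conditions (11.2), and thromboembolic events and bone pain (11.3). Because 11.1 tabulates the highest grade per subject, a mild event on placebo that recurs as a severe one on luspatercept would appear as severe under Placebo.

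The baseline rule affects every threshold expressed relative to baseline: leukocytes, platelets and creatinine (11.4.1), blood pressure rises (11.5) and QTcF increase (11.6). In the cross-over column these would combine drift over the placebo period with any effect of luspatercept.

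**Working it through.** The plan states no figure on this point, so the first check is to apply the written rules to one subject.

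**1. One cross-over subject.** First dose is placebo and last dose is luspatercept. The SAP 11.1 window therefore runs from the first placebo dose to 63 days after the last luspatercept dose, and covers both periods. The subject belongs to three columns.

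| Onset of event | In window? | Placebo | Cross-over only | Including cross-over |
|---|---|---|---|---|
| On blinded placebo | yes | counted | counted | counted |
| On open-label luspatercept | yes | counted | counted | counted |

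With a boundary at cross-over, the first row would count under Placebo only and the second row in the two luspatercept columns only.

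**2. Baseline.** SAP 4.1 puts unblinding at the last subject's 48 weeks after first dose, and the Open-label Phase follows it. At cross-over the SAP 5.1 baseline is therefore about 48 weeks old or more.

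**3. Share of Placebo person-time that is luspatercept time.** Let c be the fraction crossing over, DB the blinded weeks and OL the open-label weeks, so OL = total − DB. Taking DB as the same for all placebo subjects, and no further time for those who do not cross over:

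share = c × OL / (DB + c × OL)

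The 48 weeks is the length of the blinded Treatment Period, and 228 is the last week in the SAP 5.1 interval list. The other inputs are assumptions.

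- Low: DB 96, total 144, OL 48, c = 0.5: 24 / (96 + 24) = 20%.
- Middle: DB 72, total 192, OL 120, c = 0.75: 90 / (72 + 90) = 56%.
- High: DB 48, total 228, OL 180, c = 0.9: 162 / (48 + 162) = 77%.

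**4. What this does to an incidence.** Use the middle case with constant event rates (assumed); 72 weeks = 72/52 years and 120 weeks = 120/52 years.

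- With the boundary, 0.05 per person-year on placebo: 1 − exp(−0.05 × 72/52) = 6.7%.
- No boundary, 0.05 on both products: 0.25 × 6.7% + 0.75 × [1 − exp(−0.05 × 192/52)] = 14.3%.
- No boundary, 0.05 on placebo and 0.15 on luspatercept: 0.25 × 6.7% + 0.75 × [1 − exp(−0.05 × 72/52 − 0.15 × 120/52)] = 27.2%.

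The rise from 6.7% to 14.3% is longer follow-up alone. The further rise to 27.2% is drug effect shown under Placebo.

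**The case against.** The strongest reply is that no sentence in the SAP assigns open-label events to Placebo. Separate cross-over columns make most sense if events are split by period, SAP 5.2.2 groups subjects by the product they received, and table shells may apply the split. A reader might infer that the sponsor planned to count luspatercept events as placebo events. The documents do not support that: this is a missing rule, and the intent may have been otherwise. The gap remains, because 5.2.2 assigns subjects, not events or periods, a cross-over subject received both products, and the written window gives the result in the table above.

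Three other stronger readings also fail.

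- A reader might take the sentence on using all collected records as proof for adverse events. It names adverse events as an exception, so it bears on laboratory, vital-sign and ECG summaries. The adverse event problem rests on the 11.1 window.
- A reader might infer that the randomized safety comparison is contaminated. SAP 4.1 says that the primary CSR plan covered data only up to unblinding, and cross-over came afterwards.
- A reader might infer that drug effects disappear. Open-label events also appear in the two luspatercept columns that include cross-over subjects, and deaths and events of special interest are listed.

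It is also fair that the SAP 5.1 baseline is a general default, and that a new one is not always available. In the blinded periods, Protocol Table 3 schedules an on-treatment ECG only at Dose 6. Under Protocol 6.4 the open-label entry ECG is for placebo subjects already in follow-up. SAP 11.4 notes that open-label laboratory data are local only, so a reset baseline would still mix laboratories.

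**Conclusion.** The concern stands for the final CSR safety tables. The SAP gives no cross-over boundary for safety windows, exposure or baseline, and its written rules put the same events of a cross-over subject in the Placebo column and in both luspatercept columns that include that subject. The consequence is a misleading Placebo column and blurred cross-over columns. No data are lost, and the primary CSR is untouched.

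The size cannot be fixed from the documents, which give neither the number crossing over nor the time on each product. The 20% to 77% range is conditional on the assumed inputs, and the incidences also assume constant rates. A share worked out for cross-over subjects alone should not be read as the share of the whole column, which also holds subjects who never crossed over. Even the low end is enough to matter for uncommon serious events, and the remedy is cheap, so the plan should be changed.

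**What to change.** 1. **Placebo column (SAP 11, 11.1, 9.1).** End the treatment-emergent, laboratory, vital-sign and ECG windows at the earlier of the last placebo dose plus 63 days and the day before the first luspatercept dose. End exposure at the earliest of the last placebo dose plus 20 days, death, and the day before the first luspatercept dose.
2. **Cross-over columns.** Start windows and exposure at the first luspatercept dose. In the column that combines all luspatercept recipients, count only luspatercept-period data for cross-over subjects. An event starting after that dose belongs here even if it falls within 63 days of the last placebo dose. Apply the same date to late events suspected to be related.
3. **Baseline (SAP 5.1).** For the cross-over columns, use the last value on or before the first luspatercept dose. The separate leukocyte rule in 5.1 needs a counterpart. Flag parameters without a recent value before cross-over (for example ECG) and the change from central to local laboratory.

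Because follow-up will differ between columns, rates per person-year beside the incidences would help.

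The cost is a few date definitions in SAP 5.1, 9.1, 11 and 11.1, some extra programming and a second baseline for cross-over subjects. It needs no new data and no change to how subjects are managed.
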